Does an information leaflet provide an effective way of communication in the peri-procedure period? Will it help in better information delivery and hence reduce the number of avoidable postponements and delay. And does this translate to better patient satisfaction is what this study aims to see. The study is restricted to patients undergoing Head & Neck procedures under General Anaesthesia, as they form the major bulk of patients in our minor OT complex and for logistic reasons to start with a defined group of patients.

AIMS AND OBJECTIVES:

1. To reduce postponement of cases due to lack of information to patients in the pre-operative period
2. To compare satisfaction levels between patients , pre and post introduction of information leaflet

Primary end point:

To reduce postponement of cases due to lack of information to patients in the pre-operative period

Co Primary end point:

To compare satisfaction levels between patients, pre and post introduction of information leaflet.

Design of the study: Pre and post interventional model

INCLUSION CRITERIA:

All adult patients (> 18yrs), ASA I-III, undergoing elective therapeutic/diagnostic Head & Neck surgeries under General Anaesthesia in the Minor OT complex and discharged on the same day will be included. The surgeries will include Head & Neck surgeries like DL scopes, laser surgeries, EUA, excision biopsies etc.

EXCLUSION CRITERIA:

1. Patients refusing to take part in study
2. Patients undergoing emergency surgeries
3. ASA IV patients, or high risk patients planned for admission
4. Admitted patients for minor OT procedure
5. Patients not getting the Information leaflet due to any reason (in 2nd half of study)
6. Patient and his attendant, both illiterate

MATERIAL AND METHODS

After Institutional Review Board approval, all adult patients meeting inclusion criteria and undergoing surgeries in the Minor OT complex during a 6 month period will be enrolled in the study. The study will be done in two parts.

In the First half of study- planned over 2 months (Nov-Dec), feedback forms will be collected from patients at the end of minor OT procedure (Annexure 2.1) All patients, meeting inclusion criteria, at the end of the procedure prior to discharge from the minor OT will be explained about the study and they shall be given a feedback form to be filled and submitted. Also the number of postponement or rescheduling of cases will be noted.

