For our preliminary review of postponement rate as defined in our study is around 20%. We aim for a reduction of such postponement by 50%. Group sample sizes of 199 in group 1 and 199 in group 2 achieve 80.007% power to detect a difference between the group proportions of -0.1000. The proportion in group 1 (the treatment group) is assumed to be 0.2000 under the null hypothesis and 0.1000 under the alternative hypothesis. The proportion in group 2 (the control group) is 0.2000. The test statistic used is the two-sided Z-Test with pooled variance. The significance level of the test is 0.0500. Considering a 20% loss to follow up from OPD to minor OT, the sample size needed is 480 patients. On an average at least 250 patients of head neck patients undergo procedure under general anesthesia, per month (12-15 patients /day x 20 working days). With due consideration of our inclusion criteria, a two month recruitment period pre and post intervention should be adequate.

MEASUREMENTS

- No. of cases postponed pre and post introduction of the leaflet and reasons behind them
- Primary data collected will be patient satisfaction levels after the procedure (both pre and post PIL) on a 5 point Likert scale (Ranging from very poor = 0 to Excellent = 4)
- No of patients who did not receive the patient information leaflet in the OPD
- No of patients who received the PIL but did not get it along to the minor OT

STATISTICAL ANALYSIS

All Data will be analyzed using SPSS software. Likert scores will be treated as ordinal data. Proportions will be compared using chi square analysis. Additionally Multivariate logistic regression analysis will be used to assess the contribution of possible covariates, including age sex and patient knowledge on patient satisfaction. For all data P-value < 0.05 will be considered as statistical significant.

REFERENCES:

1. Beverly K. Philip MD, Day Care Surgery: The United States Model of Health Care IAAS Journal/17.4/PHILIP17.4.pdf
2. Emerging Trends in Healthcare A Journey from Bench to Bedside 17 February 2011;KPMG/ASSOCHAM
3. Jarrett, P. E. M, Day care surgery ;European Journal Of Anaesthesiology November 2001 - Volume 18 - Issue - p 32–35

Annexure 2.1

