You are invited to take part in this study & help us improve the quality of services provided to you. Your participation is completely voluntary & it will not alter the treatment given to the patient in any way. Please base your answers on today's experience at this MINOR OT COMPLEX. Just mark the option which the patient thinks is correct.

1. Patients age _____ Gender _____

2. Education: Illiterate/ school/ graduate/ post graduate (please tick patients highest qualification)

3. Are you filling this questionnaire for self or on behalf of the patient?,

If Yes (please tick your highest qualification) Education Illiterate/ school/ graduate/ post graduate

4. Is this your first visit to this Minor OT complex? Yes No

If "No" when was the last time you came here? _____

5. Were you adequately informed with regard to the fasting procedure, pre-surgery (What to eat/drink)?

Yes No Not sure

6. Were you informed about any tests (blood tests, ecg, scans,x-ray etc.) that were necessary before the procedure?

Yes No Not sure

7. If you take any medicine on a regular basis, were you informed about which medicines to continue or to avoid on the day of surgery?

Yes No Not sure

8. Did you receive enough information about the future course of action about your treatment (includes when to expect the result of today's procedure, future treatment & follow up)

Yes No Not sure

9. How was your overall satisfaction with respect to the information you were provided before the surgery?

Excellent Very good Good Poor Very Poor

10. How was your overall satisfaction with respect to the information you were provided after the surgery?

Excellent Very good Good Poor Very Poor

Annexure 2.2

You are invited to take part in this study & help us improve the quality of services provided to you. Your participation is completely voluntary & it will not alter the treatment given to the patient in any way. Please base your answers on today's experience at this MINOR OT COMPLEX. Just mark the option which the patient thinks is correct.

1. Patients age _____ Gender _____

2. Education Illiterate/ school/ graduate/ post graduate (please tick patient's highest qualification)

3. Are you filling this questionnaire for self or on behalf of the patient? If Yes (please tick your highest qualification) Education Illiterate/ school/ graduate/ post graduate

4. Is this your first visit to this Minor OT complex?, Yes No

If "No" when was the last time you came here? _____

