5. Were you adequately informed with regard to the fasting procedure, pre-surgery (What to eat/drink)?

Yes No Not sure

6. Were you informed about any tests (blood tests, ecg, scans,x-ray etc.) that were necessary before the procedure?

Yes No Not sure

7. If you take any medicine on a regular basis, were you informed about which medicines to continue or to avoid on the day of surgery?

Yes No Not sure

8. Did you receive enough information about the future course of action about your treatment (includes when to expect the result of today's procedure, future treatment & follow up)

Yes No Not sure

9. Have you received any Information leaflet at the OPD?

Yes No

If "yes "have you read the leaflet?

Yes No

If "yes "have you understood the information provided in the leaflet?

Yes No

10. What is your opinion about the leaflet?

Very Good Good Average Bad Very Bad

11. Would you recommend this leaflet to others?

Strongly recommend / will Recommend/ Neutral /recommend reluctantly/ not recommend at all

12. How was your overall satisfaction with respect to the information you were provided before the surgery?

Excellent Very good Good Poor Very Poor

13. How was your overall satisfaction with respect to the information you were provided after the surgery?

Excellent Very good Good Poor Very Poor

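### No named analysis of the co-primary satisfaction comparison uses the order of the scale or adjusts for differences between the two periods, and the added regression leaves its type, outcome item and 'patient knowledge' undefined

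*Combined protocol and SAP*

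**What the plan says.** Satisfaction is the co-primary end point, repeating the second objective: "To compare satisfaction levels between patients , pre and post introduction of information leaflet". Measurements scores it "on a 5 point Likert scale (Ranging from very poor = 0 to Excellent = 4"). Statistical Analysis then says that "Likert scores will be treated as ordinal data", that proportions will be compared by chi-square and, as an additional analysis, that "Multivariate logistic regression analysis will be used to assess the contribution of possible covariates, including age sex and patient knowledge on patient satisfaction". No ordinal test or ordinal model is named, and no cut on the 0-4 score is given.

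Each form asks about satisfaction twice. Item 9 of Annexure 2.1 (item 12 of Annexure 2.2) reads "How was your overall satisfaction with respect to the information you were provided before the surgery". Item 10 (item 13) reads "How was your overall satisfaction with respect to the information you were provided after the surgery". The plan does not say which is the end point.

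Patient knowledge appears only in the regression sentence. The nearest form items are 5 to 8, answered Yes, No or Not sure; item 5, for example, begins "Were you adequately informed with regard to the fasting procedure, pre-surgery (What to eat/drink". Annexure 2.2 item 9 also asks "have you understood the information provided in the leaflet", in the post-leaflet period only.

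**The concern.** This is a before-and-after study without randomisation, so patients in the two periods may differ in age, education, previous visits or who filled in the form. The co-primary comparison should allow for that and should use the ordering that the plan itself assigns to the scale. The named methods do neither. Chi-square ignores order and takes no covariates. The regression takes covariates, but its listed terms omit period, so it is not stated to estimate the pre/post difference at all.

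Two further gaps leave choices open until the data are in. The first is the form of the outcome: which item, and ordinal or dichotomised. The second is the knowledge covariate. If it is built from items 5 to 8 and period is then added, the model adjusts for a step on the route by which the leaflet is supposed to work. The introduction sets out that route: better information delivery, and through it, possibly, better satisfaction.

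**Working it through.** **1. The plan's own figure.** The only sample-size calculation is for postponement: 20% versus 10%, two-sided 0.05, pooled Z-test.

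n = [1.960·√(2·0.15·0.85) + 0.8416·√(0.20·0.80 + 0.10·0.90)]² / 0.10² = (0.9897 + 0.4208)² / 0.01 = 198.97, so 199 per group.

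This reproduces the stated 199 and its 80.007% power. The plan gives no figure for satisfaction. The illustrations below borrow 199 per period; all their other inputs are assumptions.

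**2. What the regression needs, against what the documents supply.**

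| Needed | Supplied |
|---|---|
| Outcome item | Two satisfaction items, neither designated |
| Model type | Logistic, binary or ordinal not stated; scores called ordinal |
| Cut, if binary | None |
| Period term | Not listed, though the covariate list is open-ended |
| Knowledge variable | Undefined; no item tests knowledge |
| Baseline items on both forms | Age, sex, education, first/repeat visit, who completed the form; only age and sex are named for the model |

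**3. How far the method matters.** Assume a pre-leaflet distribution of 2/8/40/35/15% from Very Poor to Excellent and a common odds ratio of 1.6. Multiplying the odds at each cut by 1.6 gives the post-leaflet proportions:

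- Good or better: 0.90 → odds 9 × 1.6 = 14.4 → 14.4/15.4 = 0.935
- Very good or better: 0.50 → odds 1 × 1.6 = 1.6 → 1.6/2.6 = 0.615
- Excellent: 0.15 → odds 0.1765 × 1.6 = 0.2824 → 0.2824/1.2824 = 0.220

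Simulated power with 199 per period (4,000 replicates, chi-square without continuity correction, Mann-Whitney for the ordered test):

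| Analysis | Power |
|---|---|
| Cut at Good or better | 25% |
| Cut at Very good or better | 63% |
| Cut at Excellent | 43% |
| Five-category chi-square | 50% |
| Test using the order | 71% |

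The two-proportion formula at the middle cut gives z = (0.1154 − 1.960·0.0498)/0.0495 = 0.36, or 64%, in agreement with the simulation.

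A second assumed baseline (3/10/40/30/17%, common odds ratio 1.5) gives 24%, 52% and 36% for the three cuts. From that baseline, if the gain is only at the top (post 3/10/30/32/25%), the odds ratios at the three cuts are 1.00, 1.49 and 1.63. If it is only at the bottom (post 1/4/48/30/17%), they are 2.84, 1.00 and 1.00.

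**4. Period and feeling informed in one model.** Assume 60% feel informed before and 85% after, with satisfaction of 75% if informed and 35% if not, and no other effect of the leaflet.

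- Before: 0.60·0.75 + 0.40·0.35 = 0.59
- After: 0.85·0.75 + 0.15·0.35 = 0.69
- Crude period odds ratio: (0.69/0.31)/(0.59/0.41) = 1.55; adjusted for feeling informed: 1.00

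That is the extreme case of full mediation. With 60% informed before, 70-90% after, and an odds ratio of 2-4 for being informed:

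| Direct leaflet odds ratio | Period odds ratio, unadjusted | Adjusted |
|---|---|---|
| 1.0 (none) | 1.06-1.52 | about 1.0 |
| 1.3 | 1.37-1.94 | about 1.3 |

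**The case against.** The regression is offered as an additional look at which factors go with satisfaction, not as the pre/post test. Whether better-informed patients are more satisfied is a fair question. A plan that calls its scores ordinal may also intend an ordinal model. Three stronger readings are therefore tempting but not supported:

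- *That the analysis cannot proceed without a cut-off.* Neither an ordinal logistic model nor a five-category chi-square needs one. The gap is the unstated model type. Choosing the best of three cuts would raise the false-positive rate to about 14% in the first illustration, but nothing in the plan says the team will do that.
- *That the model as written hides a real leaflet effect.* Without a period term it estimates no leaflet effect, so none can be adjusted away. The risk arises only if period is added beside the knowledge items, which the open covariate list allows but does not state. Even then the loss is total only under full mediation.
- *That every available stand-in for knowledge is changed by the leaflet.* Education and first/repeat visit are on both forms, could stand for background knowledge, and are not altered by it.

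All of this stands, and it limits the point. It does not supply what is missing: a named analysis of the co-primary comparison that uses the order and adjusts for baseline differences. Calling the scores ordinal does not name a method, and the methods that are named do not include an ordinal one.

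**Conclusion.** The point holds in this limited form and should be corrected. A co-primary end point in a non-randomised comparison is left with an order-blind test and a supplementary model that has no listed period term, no stated type, no designated outcome item and an undefined covariate.

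Under the first illustration, using the order gives 71% power against 50% for the five-category chi-square, and a cut gives anything from 25% to 63%. These figures depend on an assumed distribution and a common odds ratio, since the documents give no satisfaction data. They show that the choice matters; they do not state this trial's power. The caution about items 5 to 8 is conditional on period being in the same model, and its size depends on how much of the leaflet's effect passes through feeling informed.

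**What to change.** Before the satisfaction data are examined, replace the regression sentence with wording such as:

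*Satisfaction with pre-surgery information (0-4; item 9 of Annexure 2.1, item 12 of Annexure 2.2) will be analysed by proportional-odds logistic regression with period (pre/post leaflet) as the term of interest, adjusted for age, sex, education, first/repeat visit and whether the patient or another person completed the form. Satisfaction with post-surgery information (items 10 and 13) will be analysed in the same way as a secondary outcome.*

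Leave patient knowledge out of this model. Report items 5 to 8 by period as secondary outcomes. If the link between feeling informed and satisfaction is of interest, examine it in a separate exploratory model built from named items.

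The cost is SAP wording: every variable is already on both forms, and SPSS, the stated software, fits the model. The downside is that the proportional-odds assumption must be checked. The adjustment covers recorded differences between periods only; other changes over calendar time remain a limit of the design.

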Postponement or rescheduling of case is defined as an event when the patient who is called for his turn in minor OT is deferred for any amount of time in account of starvation not adequate, investigations not brought, medications not taken as prescribed. Any postponement in view of awaiting opinion from senior consultant , special equipment or any investigations called in view of patients clinical conditions which was not anticipated in the OPD by the surgical colleague, or due to lack of OT time will not be included.

After the initial collection of feedback over 2 months, the patient information leaflet (PIL) will be handed over to all patients planned for procedure in the minor OT complex (Second half of study). This leaflet will be handed over by the attending doctor in the Head neck OPD. The checklist pertaining to counselling at the Head neck OPD will be ticked after they are carried out. The patient will be instructed to read leaflet carefully and carry the leaflet on the day of Minor OT procedure. In the minor OT the discharge checklist in the PIL would be carried out by all concerned including the surgical, anesthesia and nursing team. A period of 1 month (Jan) will be allowed to streamline the use of patient information leaflet.

In the subsequent 2 months, Feb - Mar, the impact of use of PIL will be assessed. Firstly by noting the number of postponement or rescheduling of cases. In addition all patients meeting inclusion criteria will be given the feedback form (Annexure 2.2) at the end of their procedure in minor OT.

For patients coming to minor OT without a patient information leaflet- one would ascertain if the leaflet was handed in OPD and not brought to minor OT or if the leaflet was not handed at all. The numbers of such misses will be recorded. Patients who did not get the leaflet in the OPD will be excluded from study.

Sample size calculation:

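### The header on both feedback forms conflicts with the pre-surgery items, so it is unclear whether the pre-surgery part of the co-primary satisfaction measure includes information given in the OPD

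*Combined protocol and SAP*

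**What the plan says.** **The header.** Both annexures begin with the same line: "Please base your answers on today's experience at this MINOR OT COMPLEX". It names a day (today) and a place (the Minor OT complex).

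**When the form is filled in.** Material and Methods says that eligible patients, "at the end of the procedure prior to discharge from the minor OT will be explained about the study", and are then given the form. The second period uses Annexure 2.2, also at the end of the procedure.

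**Where the intervention is delivered.** Mostly somewhere else and earlier: "This leaflet will be handed over by the attending doctor in the Head neck OPD". Counselling is recorded there too: "The checklist pertaining to counselling at the Head neck OPD will be ticked after they are carried out". The patient then takes the leaflet away: "The patient will be instructed to read leaflet carefully and carry the leaflet on the day of Minor OT procedure". One component belongs to the procedure day: "In the minor OT the discharge checklist in the PIL would be carried out by all concerned including the surgical, anesthesia and nursing team".

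**What is rated.** The co-primary end point compares satisfaction before and after introduction of the leaflet. Each form has two satisfaction items. One reads "How was your overall satisfaction with respect to the information you were provided before the surgery" (2.1 item 9, 2.2 item 12). The other asks the same about information given after surgery (2.1 item 10, 2.2 item 13). Items 5 to 7 on both forms ask about fasting, tests and regular medicines. Annexure 2.2 alone adds items 9 to 11 on the leaflet, starting with "Have you received any Information leaflet at the OPD".

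**The concern.** Fasting, test and medicine instructions are useful only if they reach the patient before the procedure day. The background section places their delivery, and the problem the study addresses, in a busy outpatient department. The header directs the respondent to a different day and place. Someone who follows it rates what Minor OT staff said that day. Someone who follows the item wording rates the OPD information as well. Both tick the same box, and no item lets the analyst separate them.

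Satisfaction is a co-primary end point, and the Measurements section describes it as the primary data collected. If an unknown share of answers to the pre-surgery item leaves out the OPD, the before-after contrast on that item mixes the leaflet's effect with how the form was read. That cannot be repaired once the forms are collected.

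**Working it through.** **Step 1. Compare each item with the header.**

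| Item | What it asks about | Fit with header (today, Minor OT) |
|---|---|---|
| 5 to 7, both forms | Fasting, tests, medicines before surgery | Conflicts: information due earlier, in the OPD |
| 8, both forms | Future treatment, results, follow-up | Partly: may be told in the OPD or on the day |
| 2.1 item 9, 2.2 item 12 | Satisfaction with pre-surgery information | Conflicts |
| 2.1 item 10, 2.2 item 13 | Satisfaction with post-surgery information | Fits; discharge checklist is done in the Minor OT |
| 2.2 item 9 | Leaflet received at the OPD | Conflicts openly |

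The OPD visit and the procedure are separate contacts: the leaflet is to be carried on the procedure day, and the sample size section allows 20% loss between the two.

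**Step 2. Effect on the contrast.** For the pre-surgery item, let a1 and a2 be the proportions dissatisfied in the two periods among respondents who include the OPD. Let b be the proportion among those who rate only the Minor OT day, taken as unaffected by the leaflet. Let s1 and s2 be the shares who follow the header. Then

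observed difference = (1 − s2)(a2 − a1) + (s1 − s2)(a1 − b).

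- If s1 = s2 = s, the second term vanishes and the effect shrinks by the factor (1 − s).
- If s1 and s2 differ, the second term can have either sign. Only Annexure 2.2 puts OPD and leaflet questions immediately before the satisfaction items, so s2 < s1 is plausible.

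Example, all values assumed: a1 = 25%, a2 = 13%, s1 = 50%, s2 = 10%. The observed difference is 0.9 × (−0.12) + 0.4 × (0.25 − b) = −0.108 + 0.4(0.25 − b). It equals the true −0.12 when 0.25 − b = −0.03, that is b = 28%. Below 28% the effect is understated; above 28% it is overstated. The documents say nothing about b, s1 or s2.

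**Step 3. Power, for illustration.** For the two-sided pooled z-test with n per group and p̄ the mean of p1 and p2,

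power = Φ{[|p1 − p2|√n − 1.96√(2p̄(1 − p̄))] / √(p1(1 − p1) + p2(1 − p2))}.

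The plan's own figure first (postponement, 0.20 against 0.10, n = 199): (1.4107 − 0.9897)/0.5 = 0.842, so power is 80.0%. This agrees with the stated 80.007%.

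The plan gives no effect size for satisfaction. The two assumed scenarios below use n = 199 and equal s in both periods:

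| Share s | p2 if dissatisfied 25% falls to 13% | Power | p2 if satisfied 50% rises to 65% | Power |
|---|---|---|---|---|
| 0% | 13.0% | 86.5% | 65.0% | 86.0% |
| 10% | 14.2% | 77.7% | 63.5% | 77.8% |
| 25% | – | – | 61.25% | 61.8% |
| 30% | 16.6% | 54.2% | – | – |
| 50% | 19.0% | 30.3% | 57.5% | 32.2% |

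In the first scenario p2 = 25% − 12%(1 − s); in the second p2 = 50% + 15%(1 − s). The rates, the share s and the split of the scale into two categories are all assumptions. The plan treats the Likert scores as ordinal and states no cut-off.

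**The case against.** The strongest reply is that the header is loose wording which the items override.

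- **The header contains no word of exclusion.** A reader might infer that respondents are told to rate only the Minor OT day. The text does not say so. This stands.
- **The items name their own object.** They ask about information before or after surgery, without limit of day or place, and many people answer the specific question. Item 4 asks about earlier Minor OT visits, so the header may simply mean this procedure rather than a previous one. This is a fair reading, and it means the share who follow the header could be small. It does not remove the conflict, since the header still names a place where the leaflet is not given.
- **Part of the intervention lies inside the header's frame.** The leaflet is brought along on the day and its discharge checklist is completed in the Minor OT. A reader might infer that the whole co-primary measure misses the intervention. The documents do not support that: the post-surgery item fits the header, and the pre-surgery item asks directly about information given beforehand.
- **The direction of bias is not established.** A reader might infer a pull towards zero because the header is the same in both periods. That needs equal shares following it, and the leaflet questions in Annexure 2.2 make equality doubtful. This stands.
- **The power figures are not evidence about this study.** The 199 per group was sized for postponement. This also stands; the figures show sensitivity only.

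**Conclusion.** The concern holds as an ambiguous recall frame. The header conflicts with items 5 to 7, with the pre-surgery satisfaction item on both forms, and with 2.2 item 9. The form does not record which frame a respondent used, so the pre-surgery part of the co-primary measure cannot be read with confidence as satisfaction with information that includes the OPD.

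Respondents who follow the header dilute the leaflet effect, but how many do so, and whether the share is the same in both periods, is unknown. The size and net direction of bias are therefore unknown. A reader might go further and call a null result uninterpretable. That does not follow, because the share could be close to zero.

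The textual conflict rests on no assumption. Every quantity in the dilution and power illustrations does, apart from the 199 per group, the 5% level and the test, which are borrowed from the postponement calculation. The change is worth making because the measure is co-primary, the ambiguity cannot be resolved afterwards, and the correction is small.

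**What to change.** Change both annexures, with identical wording, before the first form is used in November:

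1. Replace the header with a frame covering all information received about this procedure, from the OPD visit at which it was booked until discharge.
2. For items 5 to 7 and the pre-surgery satisfaction item (2.1 item 9, 2.2 item 12), specify: *from the OPD booking until you were called for the procedure*.
3. For the post-surgery satisfaction item only (2.1 item 10, 2.2 item 13), specify: *after the procedure, before discharge*.
4. Leave item 8 under the general frame. Follow-up plans may be explained in the OPD, and restricting the item to the post-procedure period would exclude that information.

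Both forms must change together. Altering the wording between the two periods would confound the comparison. A shared frame reduces the cueing from items 9 to 11 of Annexure 2.2 but does not remove it, and this should be acknowledged when the satisfaction results are interpreted.

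The cost is a few lines of wording and re-approval of the annexures. No extra patients, visits or staff are needed.

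### Item 7 of both feedback forms (regular medicines) has no not-applicable answer, so patients on no regular medicines cannot be told apart from medicine takers and any pre/post comparison of the item is diluted or biased

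*Combined protocol and SAP*

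**What the plan says.** Item 7 has the same wording and the same answers in Annexure 2.1 (before the leaflet) and Annexure 2.2 (after it): "If you take any medicine on a regular basis, were you informed about which medicines to continue or to avoid on the day of surgery", with the options "Yes No Not sure". The opening text of both forms tells the respondent: "Just mark the option which the patient thinks is correct". There is no filter question, skip instruction or not-applicable box. Medicine use is recorded neither elsewhere on the forms nor in the Measurements list.

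Three other places bear on the point:

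- **Statistical Analysis** plans a logistic regression of satisfaction on "possible covariates, including age sex and patient knowledge on patient satisfaction". It does not say which items make up patient knowledge or how they are scored.
- **The definition of postponement** (Material and Methods) counts deferrals for "starvation not adequate, investigations not brought, medications not taken as prescribed".
- **Measurements** lists "No. of cases postponed pre and post introduction of the leaflet and reasons behind them", which is a record separate from the feedback form.

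**The concern.** The item joins a condition (takes regular medicine) to a question (was told what to do with it) and records only the answer to the question. Adults of ASA class I to III are eligible, so some will take no regular medicine. Such a patient may tick No because nobody spoke about medicines, tick Yes or Not sure, or leave the item blank. A No from a properly managed non-taker then looks the same as a No from a taker who was not instructed.

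Item 7 is the only question on either form about whether medication instructions reached the patient, and the Background names medication among the instructions that patients do not follow adequately. It is therefore a natural item to compare before and after the leaflet. Without a record of medicine use, such a comparison cannot be restricted to the patients it concerns, and a change in case mix between the two periods cannot be checked. The information cannot be recovered from the forms after collection.

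**Working it through.** **The plan's own figure.** The only computed figure in the plan is the sample size for postponement. With 0.20 against 0.10, two-sided alpha 0.05, 80% power and pooled variance:

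n = [1.960 × √(2 × 0.15 × 0.85) + 0.842 × √(0.20 × 0.80 + 0.10 × 0.90)]² / 0.10² ≈ 199 per group.

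Power at 199 per group is 80.007%, as stated. Item 7 does not enter this calculation.

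**Inputs for item 7.** None is given in the documents, so all are assumptions:

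- m, the share of patients on regular medicines: 40%, with 30% and 60% as a range
- t, the true informed rate among takers: 60% before and 90% after the leaflet
- b, the share of non-takers who leave item 7 blank: 0, one half or all; the rest tick No

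**Formula.** Recorded Yes among those who answer = m·t / [m + (1 − m)(1 − b)].

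**Dilution at m = 40%:**

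| Non-takers | Before | After | Recorded rise |
|---|---|---|---|
| All tick No (b = 0) | 0.24/1.00 = 24% | 0.36/1.00 = 36% | 12 points |
| Half blank (b = 0.5) | 0.24/0.70 = 34.3% | 0.36/0.70 = 51.4% | about 17 points |
| All blank (b = 1) | 0.24/0.40 = 60% | 0.36/0.40 = 90% | 30 points |

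**Range over m.**

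- At 30% takers the rise is 9 points with no blanks (18% to 27%) and 13.8 with half blank (0.18/0.65 to 0.27/0.65).
- At 60% takers it is 18 points with no blanks (36% to 54%) and 22.5 with half blank (0.36/0.80 to 0.54/0.80).
- If all non-takers leave it blank, it is 30 points whatever m is.

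**Non-takers who tick Yes.** If all non-takers answer and a share y of them tick Yes, recorded Yes = m·t + (1 − m)·y. With y the same in both periods, the change is m × (0.90 − 0.60) = 0.40 × 0.30 = 12 points whatever y is. Dilution therefore does not require that non-takers tick No, only that they answer alike in both periods.

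**Bias if the share of takers drifts.** Hold t at 60% and let m fall from 45% to 35%.

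- All non-takers tick No: 0.45 × 0.60 = 27% to 0.35 × 0.60 = 21%, a 6-point fall with no change in communication.
- Half blank: 0.27/0.725 = 37.2% to 0.21/0.675 = 31.1%, also about 6 points.
- All blank: 60% in both periods, no bias.

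**Bias if answering changes.** With 60% non-takers, if a quarter of them move from No to Yes once they have been handed a leaflet, recorded Yes rises by 0.60 × 0.25 = 15 points with no change among takers.

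**The case against.** The strongest reply is that the flaw is small and its consequences are easily overdrawn. Much of this stands.

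- **Blanks.** An item that opens with a condition invites a non-taker to skip it. If all non-takers do, the full 30-point change is kept. This stands as a limit on the size. It does not remove the flaw: the form tells respondents to mark an option, the plan states no rule for missing answers, and a blank from a non-taker cannot be told from a blank left by a taker.
- **Role of item 7.** A pre/post comparison of this item is not listed under Measurements. At most it falls under the general sentence on comparing proportions by chi-square. This stands, and it keeps the point away from the main endpoints.
- **The satisfaction model.** A reader might infer that the flaw corrupts the patient knowledge covariate. The documents do not support that as a finding. The covariate is tied to no item. Items 5 to 8 are its likely source because they are the information items common to both forms, but they ask whether information was given and do not test knowledge. Nothing shows by how much a coefficient would move. What holds is conditional: if item 7 is included, non-takers would be misclassified.
- **Postponements.** A reader might also infer that the form hides who was at risk of a medication postponement. This does not hold. The definition counts "starvation not adequate, investigations not brought, medications not taken as prescribed", and the Background speaks of medicines due on the day of the procedure; neither is limited to regular medicines. Takers of regular medicines are therefore not clearly the at-risk group. Reasons for postponement are recorded apart from the form, and the planned comparison uses all qualifying postponements over all patients.

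**Conclusion.** The point holds as a questionnaire flaw with limited reach. Both forms mix patients on no regular medicines with takers, and the mixture cannot be undone after collection. If non-takers answer alike in both periods, the effect on a pre/post comparison of item 7 is dilution. If their share or their way of answering changes, it is bias in either direction.

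On assumed inputs (40% takers, true informed rate rising from 60% to 90%), the recorded rise lies between 12 and 30 points, depending on how many non-takers leave the item blank. With 30% to 60% takers the lower end is 9 to 18 points. The documents give no basis for choosing within these ranges.

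The primary postponement comparison, its 199 per group and its 80.007% power are unaffected. Any effect on the satisfaction model depends on a definition of patient knowledge that the plan has yet to give. The change is still worth making, because it costs almost nothing before the first period and cannot be made afterwards.

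**What to change.** 1. Add the response *I take no regular medicines* to item 7 on both Annexure 2.1 and Annexure 2.2 before the first period starts, so that the forms stay identical on this item.
2. State in Statistical Analysis that item 7 is analysed among medicine takers only, and report the share of takers in each period.
3. If item 7 is used in patient knowledge, say so and score the measure over the items that apply to each patient, for example the proportion of applicable items answered Yes. Non-takers then stay in the model.

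No separate denominator for medication postponements is needed.

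The cost is one tick-box per form, a short addition to the analysis text and a smaller denominator for item 7. The smaller denominator need not cost power. Assume 199 patients per period, half of them takers, and a true rise from 60% to 80%. The takers-only comparison (about 100 per period) has power 0.874. With all patients answering, power is 0.553 if every non-taker ticks No, 0.531 if half tick Yes, and 0.80 if all tick Yes. No extra patients, visits or staff are needed.
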